4. INVESTIGATIONAL PLAN

4.1. Overall Study Design and Plan

This is a Phase I double-blind, randomized, placebo-controlled study in 50 healthy adolescents and children, 9-17 years of age, who are in good health and meet all eligibility criteria. The study is designed to assess the safety and immunogenicity of a prime-boost regimen of H3N2 M2SR intranasal influenza vaccine followed by licensed inactivated QIV boost administered IM. Group A will receive one dose of M2SR intranasally on Day 1 and one dose of QIV on Day 92. Group B will receive one dose of saline intranasally on Day 1, and one dose of QIV on Day 92. See [Table 1](#) for the randomization scheme for this trial.

The two study arms will be enrolled and vaccinated concurrently. Enrollment was paused in November 2018 until the spring of 2019 to ensure all subjects received seasonal QIV vaccine prior to the beginning of the influenza season. An interim analysis of safety and immunogenicity data through the Day 113 visit will be performed for all subjects enrolled in 2018. For details on changes to the study design and planned analyses see [Section 12](#).

Reactogenicity will be measured by the occurrence of solicited upper respiratory (local) and systemic reactions from the time of the experimental (first) study vaccination through 7 days after vaccination and a respiratory tract assessment at 7 days post vaccination (Visit 02). Unsolicited non-serious AEs will be collected from the time of the first study vaccination through approximately 21 days after the first study vaccination. SAEs will be collected from the time of the first study vaccination throughout the entire study. AESIs (wheezing and otitis media) and NOCMC will be documented and reported from the time of first study vaccination through approximately 3 months after first study vaccination.

Immunogenicity testing will include performing HAI, neutralization, and nasal secretory IgA (sIgA) assays for secondary endpoints. If significant responses are observed to be induced by H3N2 M2SR vaccination, then HA/NA ELISA, IFN- γ ELISPOT and CFSE dilution/ICS assays will also be performed (see [Section 8.3](#) for further details). If performed, analyses for these assay results will be described in an addendum for this SAP.

Serum for HAI, HA/NA ELISA and neutralization assays will be obtained on Day 01 (pre-vaccination), Days 08, 22, and 57 after the first vaccination, immediately prior to the 2nd study vaccination (Day 92), and on Day 22 after the 2nd vaccination. Nasal swabs for sIgA will be collected on Day 01 (pre-vaccination), Days 08, 22, and 57 after the first vaccination, immediately prior to the 2nd vaccination (Day 92), and on Day 22 after the 2nd vaccination. PBMC for T cell functional assays (IFN- γ ELISPOT and CFSE dilution/ICS assays) will be harvested on Day 01 (pre-vaccination), Days 08, 22, and 57 after the first vaccination, immediately prior to 2nd vaccination (Day 92), and on Day 22 after the 2nd vaccination.

The duration of this study for each subject will be approximately 13 months.

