Two major types of influenza vaccines have been developed and widely utilized. The inactivated influenza vaccines (IIV) contain primarily HA protein (and some variable NA protein levels that co-purify with HA during manufacture). The HA is derived from 3 (trivalent vaccine) or 4 (quadrivalent vaccine [QIV]) strains representing the major early circulating viral pathogens each season. IIV induce HA type-specific antibodies, measurable in highly standardized hemagglutination inhibition (HAI) in vitro assays. An HAI titer of at least 1:40 is known to be associated with protection against influenza strains expressing the specifically targeted matching HA sequences. IIV can be highly protective if given annually to young and middle-aged populations but are less effective in infants, the elderly and the immunosuppressed. Higher dose IIV, IIV including adjuvants and novel vaccines have been designed to enhance immunity in these special populations.

Live attenuated influenza vaccines (LAIV) are reassortment viruses generated with genomic segments expressing nonstructural proteins with attenuating mutations and HA/NA-encoding segments from seasonally circulating viral strains. Flumist, the only previously licensed LAIV, is delivered intranasally. Work led by [name] and our SLU Center for Vaccine Development (SLUCVD) demonstrated that LAIV vaccination was more effective in children than IIV vaccination. The improved efficacy in children is most likely due to the induction of a better combination of serum antibodies, secretory IgA (sIgA) and cell-mediated immunity (CMI); i.e., a more complete immune response than is seen in children given IIV. In adults LAIV is also effective, however several comparative studies have suggested equal efficacy or a modest advantage to IIV. Of interest, HA-specific serum HAI responses induced by LAIV in adults have not been highly predictive of protective immunity, further suggesting that either sIgA and/or CMI can be important. In addition, inducing antibodies directed against highly conserved HA stem epitopes instead of highly variable HA head epitopes is another possible explanation for the improved protection that has been induced by LAIV. Prime/boost strategies using 2 different heterotypic pandemic influenza vaccines have led to more broadly reactive antibody responses, and is another promising area for influenza vaccine research focusing on the development of universally protective novel vaccines.

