3.2.2. Secondary

Immunogenicity:

- For HAI and Neutralizing antibody responses, percentage of subjects achieving seroconversion (defined as either a pre-vaccination titer $<1:10$ and a post-vaccination titer $\geq 1:40$, or a pre-vaccination titer $\geq 1:10$ and a minimum four-fold rise in post-vaccination antibody titer) against H3N2 M2SR-like and H3N2 QIV-like viruses at approximately 7, 21, and 56 days following receipt of the first study vaccination and immediately prior to and approximately 21 days following receipt of QIV.
- For HAI and Neutralizing antibody responses, percentage of subjects achieving a serum antibody titer of 1:40 or greater against the H3N2 M2SR-like virus and the H3N2 QIV-like virus at baseline and approximately 7, 21, and 56 days following receipt of the first study vaccination and immediately prior to and approximately 21 days following receipt of QIV.
- For HAI and Neutralizing antibody responses, the geometric mean titers (GMTs) and geometric mean fold rise (GMFR) to H3N2 M2SR-like virus and H3N2 QIV-like virus at baseline and approximately 7, 21, and 56 days following receipt of the first study vaccination and immediately prior to and approximately 21 days following receipt of QIV.
- GMT and GMFR of nasal sIgA responses directed against the H3N2 M2SR virus and the H3N2 QIV virus measured by EPT(ELISA) with and without normalization to total sIgA at baseline and approximately 7, 21, and 56 days following receipt of the first study vaccination and immediately prior to and approximately 21 days following receipt of QIV.
- Frequency of influenza H3 HA-specific (H3 M2SR-like and QIV-like viruses) and conserved internal viral protein-specific IFN- γ ELISPOT responses at baseline and approximately 7, 21, and 56 days following receipt of the first study vaccination and immediately prior to and approximately 21 days following receipt of QIV.

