Summaries of the frequency of influenza H3 HA-specific (M2SR-like and QIV-like viruses) and conserved internal viral protein-specific IFN- γ producing T-cells will include the mean (or geometric mean if data are log-normally distributed) and corresponding 95% confidence interval as well as the median, minimum, and maximum values. Fold rise from baseline will be summarized by arithmetic or Williams mean [4] if data are approximately normally or log-normally distributed, respectively, or median if data are not approximately normally distributed by inspection. Differences in frequency between the study groups will be presented. Differences in QIV-like strains will be calculated based on results to the year-matched strain. Sum Test, as appropriate. Summaries of IFN- γ producing T cells are presented in [Table 34](#), [Table 35](#), [Table 36](#), and [Table 37](#).

Figures depicting the GMT (HAI, MN, sIgA) or frequency (IFN- γ producing T cells) for each strain and assay over time will be presented beginning with [Figure 2](#) and continuing through [Figure 13](#) (GMTs), and [Figure 14](#), [Figure 15](#), [Figure 16](#), and [Figure 17](#) (frequencies).

Reverse cumulative distribution (RCD) plots will be presented for each assay (HAI, MN, and sIgA) and strain generated with separate panels for each visit, and separate curves within each panel for each study arm and overall. HAI and MN antibody titers for the M2SR-like and QIV-like A/H3N2 strains are shown beginning with [Figure 18](#) and continuing through [Figure 29](#).

The spearman correlation and corresponding p-value between strains for each assay (HAI, MN, relative and specific sIgA, and IFN- γ T cell responses) will be calculated at each time point within each study arm and

overall. The correlations will be depicted in scatter plots as [Figure 30](#), [Figure 31](#), [Figure 32](#), [Figure 33](#), [Figure 34](#), and [Figure 35](#).

The spearman correlation and corresponding p-value between HAI and MN antibody titers for each strain (M2SR-like and QIV-like A/H3N2 (within and between strains)) will be calculated at each time point within each study arm and overall. The correlation will be depicted in scatter plots in [Figure 36](#) and [Figure 37](#). The spearman correlation of T cell responses between peptides tested will be presented for each strain as shown in [Figure 38](#) and [Figure 39](#).

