8.3. Exploratory Immunogenicity Analyses

Completion of exploratory immunogenicity assays are contingent upon seeing scientifically relevant increased response in the M2SR-vaccinated group for the indicated assay, as determined by the scientific lead (SL) and principal investigator (PI) at the time of primary and secondary analyses.

HA ELISA reactivity with groups 1 and 2 HA stem domains of the viral hemagglutinin and serum anti-NA antibody titers to N1 and N2 neuraminidases measured by ELLA or ELISA will be completed if a scientifically relevant increase in rates of either seroconversion or 4-fold rise in either M2SR or QIV matched H3HA-specific HAI and/or MN assays in the M2SR vaccinated arm are observed after the H3N2 M2SR vaccination.

Anti-NA IgA responses to N1 and N2 neuraminidases will be assessed if a scientifically relevant increase in GMFR is observed for M2SR matched nasal sIgA is observed in the M2SR vaccinated arm after the H3N2 M2SR vaccination.

CD4⁺ and CD8⁺ T cell responses to the H3 HA present in the M2SR vaccine and pools of highly conserved Influenza A T cell epitopes will be assessed if a scientifically relevant increase in either H3 HA-specific or conserved peptide epitope-specific IFN- γ producing T cells is observed post M2SR vaccination for participants who received M2SR compared to participants who received placebo.

Planned analyses for any exploratory cellular immunology assays that are conducted based on the criteria above will be presented in an addendum to this SAP.

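### SAP 4.1 makes the IFN-gamma ELISPOT conditional on undefined significant responses, against its unconditional secondary status in the rest of both documents

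*SAP*

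**What the plan says.** SAP 4.1 sorts the assays into two groups. The first serves the secondary endpoints: "Immunogenicity testing will include performing HAI, neutralization, and nasal secretory IgA (sIgA) assays for secondary endpoints". The second is conditional: "If significant responses are observed to be induced by H3N2 M2SR vaccination, then HA/NA ELISA, IFN- γ ELISPOT" and the CFSE/ICS assays are then also to be run, and the reader is sent to SAP 8.3 for detail. The analysis of the second group is postponed: "If performed, analyses for these assay results will be described in an addendum for this SAP".

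SAP 3.2.2 places ELISPOT differently. Its last secondary endpoint is "Frequency of influenza H3 HA-specific (H3 M2SR-like and QIV-like viruses) and conserved internal viral protein-specific" IFN-gamma ELISPOT responses, at baseline and five later time points, with no condition attached. Protocol 3.2.2 lists the same endpoint in the same way.

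The second of the two secondary objectives (Protocol 3.1.2, SAP 3.1.2) concerns cellular responses to M2SR. ELISPOT is the only secondary endpoint that addresses it. The other T-cell assay, CFSE dilution, is exploratory.

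**The concern.** A statistician who works from SAP 4.1 would treat ELISPOT as an exploratory assay: run it only if something else looks positive, and write its analysis afterwards. Two things would follow. The secondary cellular objective could end the trial with no data. Or, if data exist, they would exist because other results were favorable, and the analysis would have been written after those results were seen. A descriptive estimate reported under that rule is a selected one.

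The protocol gives a reason to want the T-cell result whatever the antibody results are. Protocol 2.1 says of live vaccine that "HA-specific serum HAI responses induced by LAIV in adults have not been highly predictive of protective immunity", and it names mucosal IgA and cell-mediated immunity as possible explanations. It also reports T-cell responses in children after live but not inactivated vaccine. A T-cell response without a clear antibody response, serum or mucosal, is one that the condition in 4.1 could leave unmeasured.

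**Working it through.** No figure in the plan is in dispute. The check is to set the places that mention ELISPOT side by side.

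1. **Endpoint lists.** All five exploratory endpoints in Protocol 3.2.3 and SAP 3.2.3 carry a note making them contingent on earlier results. None of the five secondary endpoints in 3.2.2 of either document does. ELISPOT is in the second set.
2. **Protocol analysis section.** Protocol 11.4.3 commits to descriptive ELISPOT summaries among the secondary analyses. Protocol 11.4.4 applies the contingency to exploratory studies only.
3. **SAP outside 4.1.** SAP 4.5.1 says that IFN-gamma T-cell frequencies will be reported. SAP 6.2 holds the final analysis until all secondary immunogenicity data are in, and reserves the addendum for exploratory measures. SAP 6.3.1 names IFN-gamma T cells among the assays for which mITT membership is assessed. SAP 8 specifies the ELISPOT summaries, and SAP 8.2 says every secondary measure is summarized that way. Tables 34-37, Figures 14-17 and Listing 10 are laid out for the results.
4. **The section that 4.1 cites.** SAP 8.3 contains no trigger for ELISPOT. It uses ELISPOT as the trigger for something else: the CD4/CD8 responses "will be assessed if a scientifically relevant increase in either H3 HA-specific or conserved peptide epitope-specific" IFN-gamma producing T cells is seen in M2SR recipients compared with placebo. That rule needs ELISPOT to have been run, whereas 4.1 puts both assays behind one condition.
5. **Meaning of significant.** Protocol 11.1 and SAP 6.8 say that the study tests no specific null hypothesis. SAP 8.3 uses a different standard, scientific relevance as judged by the scientific lead and principal investigator, and applies it to exploratory assays. No test, threshold, assay, strain or visit is given for the condition in 4.1.
6. **Record of a decision.** SAP 12 lists one change of contingency, for the anti-NA assays. It lists none that made ELISPOT conditional.

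Because the trigger is undefined, the chance of meeting it cannot be calculated. As an illustration only, under assumptions that are not in the documents, suppose it meant one two-sided 0.05 test of seroconversion with 25 per arm and a true difference of 0.20. The chance of meeting it is the sum, over all rejecting pairs (x, y), of Bin(x; 25, p0) × Bin(y; 25, p0 + 0.20):

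- p0 = 0.20: 35% (chi-square), 23% (Fisher)
- p0 = 0.05: 56% (chi-square), 37% (Fisher)
- p0 = 0: 77% (chi-square), 38% (Fisher)

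The range of 23% to 77% shows that the undefined word matters. It is not an estimate for this trial, where several assays, strains and visits might each satisfy the condition, and where a judgment might replace a test.

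**The case against.** The strongest reply is that this is a slip in a design overview. Every operative section treats ELISPOT as unconditional, the final analysis waits for all secondary data, and PBMC are collected in any case. That stands. It is why the consequence is stated as a possibility and why the point is an inconsistency rather than a chosen design. It does not remove the need to correct 4.1, which is explicit on all three matters: which assays are secondary, when ELISPOT is run, and where its analysis is described. Protocol 11.4 and 15.4 do name HAI, MN and sIgA as the secondary assays whose results precede the topline tables. That concerns timing and does not make ELISPOT conditional.

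A reader might also infer stronger things that the documents do not support.

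- **That the rule is circular.** Running ELISPOT after other assays, and CFSE after ELISPOT, would be a sequence. SAP 4.1 and 8.3 disagree; neither is circular.
- **That any T-cell response without an HAI rise would be missed.** Nasal sIgA is unconditional in 4.1, so a mucosal response could satisfy the condition. The exposed case is a T-cell response without a clear serum or mucosal response.
- **That children give 96 mL of blood for nothing.** The figure 6 × 16 = 96 mL is a maximum. PBMC collection stops after Day 57 if hemoglobin stays low, which leaves 4 × 16 = 64 mL. Residual PBMC are also kept for future research (Protocol 14.8).
- **That subjects with a zero baseline drop out of the fold rise.** No section says so. SAP 3.3 states a detection limit of zero only for the conserved internal-protein responses. SAP 8 says "Fold rise from baseline will be summarized by arithmetic or Williams mean", and the Williams mean adds one before taking logs. At most, the SAP leaves unstated whether the one is added before the ratio is formed.

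**Conclusion.** The contradiction is real and confined to one paragraph of SAP 4.1. If that paragraph governed, the single endpoint for one of two secondary objectives could go unrun or be reported selectively, and Tables 34-37, Figures 14-17 and Listing 10 could be empty. If the rest of the plan governs, nothing is lost. The documents do not say which prevails. The weight of the text favors the unconditional reading, and the conclusion assumes only that someone could reasonably follow 4.1 as written. The endpoint is descriptive, in an exploratory Phase I trial, and the primary safety analysis does not depend on it. The correction should be made before unblinded immunogenicity results are seen, because afterwards either choice would look driven by the results.

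**What to change.** In SAP 4.1, list IFN-gamma ELISPOT with HAI, neutralization and sIgA as the assays performed for the secondary endpoints. Keep the condition and the addendum for the exploratory HA/NA ELISA/ELLA and CFSE/ICS assays, and align the wording of the condition with SAP 8.3.

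If a condition on ELISPOT is really intended, amend the endpoint in Protocol 3.2.2 and SAP 3.2.2, define the trigger (assay, strain, visit and threshold) before unblinding, and record the change in SAP 12.

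While editing, add one sentence to SAP 8 saying whether the one used in the Williams approach is added before the fold rise is computed.

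The cost is SAP wording. The samples are already scheduled and the assay is already committed in the endpoint list. The downside is that ELISPOT is run even if the antibody results are null.

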4.2. Discussion of Study Design, Including the Choice of Control Groups

This protocol follows double-blind, randomized, placebo concurrent control design. Subjects receive either H3N2 M2SR or saline placebo intranasally via VaxINator device as their first study vaccination. After approximately 3 months, all subjects receive licensed QIV administered intramuscularly (IM) as the second study vaccination.

4.3. Selection of Study Population

The study population for this clinical trial is 50 male and non-pregnant female children and adolescents between the ages of 9 and 17 who are in good health and meet all eligibility criteria. Specific eligibility criteria can be found in the protocol sections 5.1 (Subject Inclusion Criteria) and 5.2 (Subject Exclusion Criteria). The subjects are recruited from the general population at the participating Vaccine Trial and Evaluation Unit (VTEU) site, Saint Louis University (SLU), which has substantial experience conducting influenza vaccine studies.

Following review of laboratory results for subjects enrolled through August 2018, it was identified that a significant portion had a drop in hemoglobin during the study. The protocol was amended to include screening for pre-existing iron deficiency anemia with ferritin and requiring both normal ferritin and HgB results for enrollment, to reduce the amount of blood collected overall, and to add a contingency regarding specimen collection. Subjects will be monitored after entry in the trial for drops in hemoglobin levels indicating anemia. If HgB levels are consistently low through the visit at approximately Day 57, the subject will no longer have PBMC samples collected at subsequent visits.

